7.2 Assessing and Recording Adverse Events

An adverse event is defined as any untoward medical occurrence in a patient or clinical investigation subject administered a pharmaceutical product and which does not necessarily have to have a causal relationship with this treatment. An adverse event can therefore be any unfavorable and unintended sign (including an abnormal laboratory finding, for example), symptom, or disease temporally associated with the use of a medicinal product or protocol-specified procedure, whether or not considered related to the medicinal product or protocol-specified procedure. Any worsening (i.e., any clinically significant adverse change in frequency and/or intensity) of a preexisting condition that is temporally associated with the use of (⁸⁹Zr-)pembrolizumab, is also an adverse event.

Changes resulting from normal growth and development that do not vary significantly in frequency or severity from expected levels are not to be considered adverse events. Examples of this may include, but are not limited to, teething, typical crying in infants and children and onset of menses or menopause occurring at a physiologically appropriate time.

Adverse events may occur during the course of the use of (⁸⁹Zr-)pembrolizumab in clinical trials or within the follow-up period specified by the protocol, or prescribed in clinical practice, from overdose (whether accidental or intentional), from abuse and from withdrawal. Adverse events may also occur in screened subjects during any pre-allocation baseline period as a result of a protocol-specified intervention, including washout or discontinuation of usual therapy, diet, placebo treatment or a procedure.

Progression of the cancer under study is not considered an adverse event unless it is considered to be drug related by the investigator.

All adverse events will be recorded from the time the consent form is signed through 90 days following cessation of treatment or the initiation of new anti-cancer therapy, whichever is earlier and at each examination on the Adverse Event case report forms/worksheets. The reporting timeframe for adverse events meeting any serious criteria is described in section 7.2.3.1.

7.2.1 Definition of an Overdose for This Protocol and Reporting of Overdose

For purposes of this trial, an overdose of pembrolizumab will be defined as any dose of 1,000 mg or greater (≥ 5 times the indicated dose). No specific information is available on the treatment of overdose of pembrolizumab. Appropriate supportive treatment should be provided if clinically indicated. In the event of overdose, the subject should be observed closely for signs of toxicity. Appropriate supportive treatment should be provided if clinically indicated.

If an adverse event(s) is associated with (“results from”) the overdose of pembrolizumab, the adverse event(s) is reported as a serious adverse event, even if no other seriousness criteria are met.

If a dose of pembrolizumab meeting the protocol definition of overdose is taken without any associated clinical symptoms or abnormal laboratory results, the overdose is reported as a non-serious Event of Clinical Interest (ECI), using the terminology “accidental or intentional overdose without adverse effect.”

All reports of overdose with and without an adverse event must be reported within 24 hours to the principal investigator (PI) and within 2 working days hours to Merck Global Safety. (Attn: Worldwide Product Safety; [contact])

7.2.2 Reporting of Pregnancy and Lactation

Although pregnancy and lactation are not considered adverse events, it is the responsibility of investigators or their designees to report any pregnancy or lactation in a subject (spontaneously reported to them) that occurs during the trial.

Pregnancies and lactations that occur after the consent form is signed but before treatment allocation/randomization must be reported by the investigator if they cause the subject to be excluded from the trial, or are the result of a protocol-specified intervention, including but not limited to washout or discontinuation of usual therapy, diet, placebo treatment or a procedure.

Pregnancies and lactations that occur from the time of treatment allocation/randomization through 120 days following cessation of pembrolizumab, or 30 days following cessation of treatment if the subject initiates new anticancer therapy, whichever is earlier, must be reported by the investigator. All reported pregnancies must be followed to the completion/termination of the pregnancy. Pregnancy outcomes of spontaneous abortion, missed abortion, benign hydatidiform mole, blighted ovum, fetal death, intrauterine death, miscarriage and stillbirth must be reported as serious events (Important Medical Events). If the pregnancy continues to term, the outcome (health of infant) must also be reported.

Such events must be reported within 24 hours to the PI and within 2 working days to Merck Global Safety. (Attn: Worldwide Product Safety; [contact])

7.2.3 Immediate Reporting of Adverse Events

7.2.3.1 Serious Adverse Events

A serious adverse event is any adverse event occurring at any dose or during any use of (^{89}Zr -)pembrolizumab that:

- Results in death;
- Is life threatening;

- Results in persistent or significant disability/incapacity;
- Results in or prolongs an existing inpatient hospitalization;
- Is a congenital anomaly/birth defect;
- Is a new cancer (that is not a condition of the study);
- Is associated with an overdose;
- Is another important medical event

Details regarding the above criteria can be found in Table 6.

Progression of the cancer under study is not considered an adverse event unless it results in hospitalization or death.

Any serious adverse event, or follow up to a serious adverse event, including death due to any cause other than progression of the cancer under study that occurs to any subject from the time the consent is signed through 90 days following cessation of treatment, or the initiation of new anti-cancer therapy, whichever is earlier, whether or not related to (⁸⁹Zr-)pembrolizumab, must be reported within 24 hours to the PI.

In the event of the occurrence of any clinical AE or abnormal laboratory test value that is serious or medically important during the course of the study or the post-treatment period, irrespective of the treatment received by the subject, the investigator is obliged to immediately inform the PI. The immediate report by the investigator to the PI shall be followed by detailed, written, reports using the SAE report form (for an “initial” SAE or for “follow-up” information on a previous SAE).

All SAEs will be reported by the PI through the web portal *ToetsingOnline* to the accredited METC that approved the protocol, within 15 days after the PI has first knowledge of the serious adverse reactions.

SAEs that result in death or are life threatening should be reported expedited. The expedited reporting will occur not later than 7 days after the responsible investigator has first knowledge of the adverse reaction. This is for a preliminary report with another 8 days for completion of the report.

Additionally, any serious adverse event, considered by an investigator who is a qualified physician to be related to (⁸⁹Zr-)pembrolizumab that is brought to the attention of the investigator at any time outside of the time period specified in the previous paragraph also must be reported immediately to the PI and Merck.

All subjects with serious adverse events must be followed up for outcome.

7.2.3.2 Suspected Unexpected Serious Adverse Reactions (SUSARs)

SUSARs will be reported through the web portal *ToetsingOnline* to the accredited METC that approved the protocol and to EudraVigilance, within 15 days after the PI has first knowledge of the SUSAR. SUSARs within this study and SUSARs of pembrolizumab in other studies will be reported separately to the METC.

7.2.3.3 Events of Clinical Interest

Selected non-serious and serious adverse events are also known as Events of Clinical Interest (ECI) and must be reported within 24 hours to the PI and within 2 working days to Merck Global Safety. (Attn: Worldwide Product Safety; [contact])

For the time period beginning when the consent form is signed until treatment allocation/randomization, any ECI, or follow up to an ECI, that occurs to any subject must be reported within 24 hours to the PI and within 2 working days to Merck Global Safety if it causes the subject to be excluded from the trial, or is the result of a protocol-specified intervention, including but not limited to washout or discontinuation of usual therapy, diet, placebo treatment or a procedure.

For the time period beginning at treatment allocation/randomization through 90 days following cessation of treatment, or 30 days following cessation of treatment if the subject initiates new anticancer therapy, whichever is earlier, any ECI, or follow up to an ECI, whether or not related to pembrolizumab, must be reported within 24 hours to the PI and within 24 hours to Merck Global Safety.

Events of clinical interest for this trial include:

1. an overdose of pembrolizumab, as defined in Section 7.2.1 - Definition of an Overdose for This Protocol and Reporting of Overdose, that is not associated with clinical symptoms or abnormal laboratory results.
2. an elevated AST or ALT lab value that is greater than or equal to 3X the upper limit of normal and an elevated total bilirubin lab value that is greater than or equal to 2X the upper limit of normal and, at the same time, an alkaline phosphatase lab value that is less than 2X the upper limit of normal, as determined by way of protocol-specified laboratory testing or unscheduled laboratory testing.*

*Note: These criteria are based upon available regulatory guidance documents. The purpose of the criteria is to specify a threshold of abnormal hepatic tests that may require an additional evaluation for an underlying etiology.

7.2.4 Evaluating Adverse Events

An investigator who is a qualified physician will evaluate all adverse events according to the NCI Common Terminology for Adverse Events (CTCAE), version 4.0. Any adverse event which changes CTCAE grade over the course of a given episode will have each change of grade recorded on the adverse event case report forms/worksheets.

All adverse events regardless of CTCAE grade must also be evaluated for seriousness.

Table 10. Evaluating Adverse Events

An investigator who is a qualified physician, will evaluate all adverse events as to:

V4.0 CTCAE Grading	Grade 1	Mild; asymptomatic or mild symptoms; clinical or diagnostic observations only; intervention not indicated.		
	Grade 2	Moderate; minimal, local or noninvasive intervention indicated; limiting age-appropriate instrumental ADL.		
	Grade 3	Severe or medically significant but not immediately life-threatening; hospitalization or prolongation or hospitalization indicated; disabling; limiting self-care ADL.		
	Grade 4	Life threatening consequences; urgent intervention indicated.		
	Grade 5	Death related to AE		
Seriousness	
A serious adverse event is any adverse event occurring at any dose or during any use of Merck product that:
 
†Results in death; or
 
†Is life threatening; or places the subject, in the view of the investigator, at immediate risk of death from the event as it occurred (Note: This does not include an adverse event that, had it occurred in a more severe form, might have caused death.); or
 
†Results in a persistent or significant disability/incapacity (substantial disruption of one’s ability to conduct normal life functions); or
 
†Results in or prolongs an existing inpatient hospitalization (hospitalization is defined as an inpatient admission, regardless of length of stay, even if the hospitalization is a precautionary measure for continued observation. (Note: Hospitalization [including hospitalization for an elective procedure] for a preexisting condition which has not worsened does not constitute a serious adverse event.); or
 
†Is a congenital anomaly/birth defect (in offspring of subject taking the product regardless of time to diagnosis);or
 
Is a new cancer; (that is not a condition of the study) or
 
Is an overdose (whether accidental or intentional). Any adverse event associated with an overdose is considered a serious adverse event. An overdose that is not associated with an adverse event is considered a non-serious event of clinical interest and must be reported within 24 hours.
 
Other important medical events that may not result in death, not be life threatening, or not require hospitalization may be considered a serious adverse event when, based upon appropriate medical judgment, the event may jeopardize the subject and may require medical or surgical intervention to prevent one of the outcomes listed previously (designated above by a †).
			
Duration	Record the start and stop dates of the adverse event. If less than 1 day, indicate the appropriate length of time and units			
Action taken	Did the adverse event cause the Merck product to be discontinued?			
Relationship to test drug	
Did the Merck product cause the adverse event? The determination of the likelihood that the Merck product caused the adverse event will be provided by an investigator who is a qualified physician. The investigator’s signed/dated initials on the source document or worksheet that supports the causality noted on the AE form, ensures that a medically qualified assessment of causality was done. This initialed document must be retained for the required regulatory time frame. The criteria below are intended as reference guidelines to assist the investigator in assessing the likelihood of a relationship between the test drug and the adverse event based upon the available information.
 
The following components are to be used to assess the relationship between the Merck product and the AE; the greater the correlation with the components and their respective elements (in number and/or intensity), the more likely the Merck product caused the adverse event (AE):
 
 
 Exposure	Is there evidence that the subject was actually exposed to the Merck product such as: reliable history, acceptable compliance assessment (pill count, diary, etc.), expected pharmacologic effect, or measurement of drug/metabolite in bodily specimen?	
 
		Exposure	Is there evidence that the subject was actually exposed to the Merck product such as: reliable history, acceptable compliance assessment (pill count, diary, etc.), expected pharmacologic effect, or measurement of drug/metabolite in bodily specimen?
Exposure	Is there evidence that the subject was actually exposed to the Merck product such as: reliable history, acceptable compliance assessment (pill count, diary, etc.), expected pharmacologic effect, or measurement of drug/metabolite in bodily specimen?			

Time Course	Did the AE follow in a reasonable temporal sequence from administration of the Merck product? Is the time of onset of the AE compatible with a drug-induced effect (applies to trials with investigational medicinal product)?
Likely Cause	Is the AE not reasonably explained by another etiology such as underlying disease, other drug(s)/vaccine(s), or other host or environmental factors

Relationship to Merck product (continued)	The following components are to be used to assess the relationship between the test drug and the AE: (continued)	
	Dechallenge	Was the Merck product discontinued or dose/exposure/frequency reduced? If yes, did the AE resolve or improve? If yes, this is a positive dechallenge. If no, this is a negative dechallenge. (Note: This criterion is not applicable if: (1) the AE resulted in death or permanent disability; (2) the AE resolved/improved despite continuation of the Merck product; or (3) the trial is a single-dose drug trial; or (4) Merck product(s) is/are only used one time.)
	Rechallenge	Was the subject re-exposed to the Merck product in this study? If yes, did the AE recur or worsen? If yes, this is a positive rechallenge. If no, this is a negative rechallenge. (Note: This criterion is not applicable if: (1) the initial AE resulted in death or permanent disability, or (2) the trial is a single-dose drug trial); or (3) Merck product(s) is/are used only one time). NOTE: IF A RECHALLENGE IS PLANNED FOR AN ADVERSE EVENT WHICH WAS SERIOUS AND WHICH MAY HAVE BEEN CAUSED BY THE MERCK PRODUCT, OR IF REEXPOSURE TO THE MERCK PRODUCTPOSES ADDITIONAL POTENTIAL SIGNIFICANT RISK TO THE SUBJECT, THEN THE RECHALLENGE MUST BE APPROVED IN ADVANCE BY THE U.S. CLINICAL MONITOR AS PER DOSE MODIFICATION GUIDELINES IN THE PROTOCOL.
	Consistency with Trial Treatment Profile	Is the clinical/pathological presentation of the AE consistent with previous knowledge regarding the Merck product or drug class pharmacology or toxicology?
The assessment of relationship will be reported on the case report forms /worksheets by an investigator who is a qualified physician according to his/her best clinical judgment, including consideration of the above elements.		
Record one of the following	Use the following scale of criteria as guidance (not all criteria must be present to be indicative of a Merck product relationship).	
Yes, there is a reasonable possibility of Merck product relationship.	There is evidence of exposure to the Merck product. The temporal sequence of the AE onset relative to the administration of the Merck product is reasonable. The AE is more likely explained by the Merck product than by another cause.	
No, there is not a reasonable possibility Merck product relationship	Subject did not receive the Merck product OR temporal sequence of the AE onset relative to administration of the Merck product is not reasonable OR there is another obvious cause of the AE. (Also entered for a subject with overdose without an associated AE.)	

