7.2.5 Sponsor Responsibility for Reporting Adverse Events

All Adverse Events will be reported to regulatory authorities, IRB/IECs and investigators in accordance with all applicable global laws and regulations. The Sponsor will inform Merck Global Safety in the appropriate timelines for reporting Adverse Events.

The PI will submit, once a year throughout the clinical trial, a safety report to the accredited METC.

This safety report consists of:

- a list of all suspected (unexpected or expected) serious adverse reactions, along with an aggregated summary table of all reported serious adverse reactions, ordered by organ system, per study.

a report concerning the safety of the patients, consisting of a complete safety analysis and an evaluation of the balance between the efficacy and the harmfulness of the medicine under investigation.

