10.3.5 Safety of the trimodality approach

Combining SBRT with surgery appears safe. At least 4 small studies have reported on patients who have undergone surgery for salvage in patients who have recurred after SBRT (42-45). Since the results of SBRT seem to be equivalent to those of surgery we believe that the delay to surgical resection is not harmful and might even be beneficial for patients. The addition of pembrolizumab to SBRT might lead to a higher rate of pneumonitis. However, the incidence of pneumonitis depends on the target volume and is rarely seen with treatment of early stage lung cancer. Because only patients with peripheral tumors are eligible for this trial and patients receive a lobectomy according to national guidelines on the treatment for NSCLC, the irradiated lung lobe will be resected and resection margins (i.e. central bronchial and vascular structures) are not involved in the radiation target volume.

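### Table 10 records causality and action taken only against the Merck product, so a trimodality safety trial does not capture attribution to SBRT, EBUS, surgery or a joint cause

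*Combined protocol and SAP*

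**What the plan says.** Sections 2.1 and 4.2.4 make the safety of the trimodality approach a primary endpoint, covering SBRT with or without pembrolizumab, followed by surgery. Section 5.2 plans 10 patients per arm.

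Causality is assessed with Table 10 in 7.2.4. The question is "Did the Merck product cause the adverse event", and one of two answers is recorded. The yes answer is labelled as a reasonable possibility of a relationship and is described by exposure, plausible timing and "The AE is more likely explained by the Merck product than by another cause". The no answer begins "Subject did not receive the Merck product OR temporal sequence of the AE onset" and ends with the case where "there is another obvious cause of the AE". The action item in the same table is "Did the adverse event cause the Merck product to be discontinued".

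Other sections are framed more widely. Section 7.1.2.1 asks for causality and for action taken in relation to trial treatment generally. The general adverse event definition in 7.2 covers events linked in time to a procedure that the protocol specifies. Section 10.3.5 states the foreseen joint risk: "The addition of pembrolizumab to SBRT might lead to a higher rate of pneumonitis".

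Several provisions depend on whether an event is judged drug-related: Table 3 in 5.6.2.1, the supportive-care guidance in 5.8.1, SUSAR reporting in 7.2.3.2, and the annual report in 7.2.5, which contains "a list of all suspected (unexpected or expected) serious adverse reactions".

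**The concern.** The trial studies a combination, but its causality form is built for a single drug. Two gaps follow.

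First, no field attributes an event to SBRT, EBUS or surgery, in either arm, and no field allows a joint cause.

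Second, the wording of the two answers leaves pneumonitis in the treated lung poorly served. Every patient in the combination arm is irradiated, so SBRT is always available as the other cause. A rater who follows the yes text must find pembrolizumab the likelier cause. A rater who follows the no text may stop once SBRT is an obvious cause. Either route can end in not related for the very event that 10.3.5 anticipates.

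What is at stake is the account of which component, or which combination, produced the toxicity, together with the provisions that depend on drug-relatedness. Attribution that is not recorded at the time is hard to reconstruct later.

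**Working it through.** The plan gives no figure on this point, so the check sets the texts side by side.

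**1. What can be attributed.** Treatments and study procedures by arm, against the causality field available:

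| Component | SBRT arm | SBRT + pembrolizumab arm | Field in Table 10 |
|---|---|---|---|
| Pembrolizumab | not given | given | yes |
| ⁸⁹Zr-pembrolizumab tracer | not given | given | unclear: the table says Merck product, whereas 7.2 and 7.2.3.1 name the tracer together with the drug |
| SBRT | given | given | none |
| EBUS | done | done | none |
| Surgery | done | done | none |

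Three components common to all 20 patients (2 × 10) have no causality field.

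**2. Label against criterion.** The yes label asks whether a relationship is reasonably possible. The yes text asks whether the drug is the likelier cause. With two plausible causes of similar weight, the label gives yes and the text does not. The no text sets a low bar for the competing cause, because it must only be obvious; it need not be sufficient or exclusive. The table's component on likely cause, which asks whether another etiology reasonably explains the event, leans the same way.

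**3. A patient in the SBRT arm with radiation pneumonitis or a surgical complication.** The patient did not receive the product, so the answer is no. That correctly answers the question asked. The relation to SBRT or surgery is left unrecorded.

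**4. A patient in the combination arm with pneumonitis in the irradiated lung.** Exposure and timing support yes. SBRT is an obvious alternative, and 4.2.4 itself describes the clinical endpoint as radiation pneumonitis. The form accepts one answer about one agent, so a joint cause has no place, and no is a permitted answer.

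**5. Where the answer goes.** Table 3 is for drug-related events. Section 5.8.1 applies when the investigator judges the event related to pembrolizumab, and releases the investigator from the guidance otherwise. SUSAR classification requires a suspected reaction. The annual list in 7.2.5 is a list of suspected reactions. Under 7.2.3.1, reporting of SAEs outside the regular time window is required only when they are judged related.

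**6. Action taken.** Section 7.1.2.1 speaks of trial treatment. Table 10 asks only whether the Merck product was discontinued. An event that interrupts SBRT, or delays or cancels surgery, has no entry in the table.

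**7. The safety rule.** The opening sentence of 8.1 is a percentage of patients with grade 3 or higher pneumonitis and carries no condition on relatedness. Read literally, the count is the same whatever Table 10 says.

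**The case against.** The case for leaving the form alone has several parts, and much of it stands.

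- *The criteria are guidance.* Table 10 says that not all criteria need be met for a yes and leaves the decision to clinical judgment. It also asks whether the event fits the known profile of the drug, which favours yes for pneumonitis: 4.1.7 reports it in 1.8% of patients treated with pembrolizumab. Miscoding is therefore possible but not compelled.
- *Events are not lost.* All adverse events are recorded and graded whatever their cause. Under 7.2.3.1 all SAEs go to the principal investigator regardless of relatedness or treatment received, and from there to the ethics committee. The annual report also includes a complete safety analysis.
- *A drug-only question suits SUSAR reporting*, which concerns the medicinal product. That is true, but it does not explain why SBRT and surgery go unattributed in a study of all three.
- *The case report forms are still to be developed* (11.1) and could add fields. Nothing in the protocol requires this, and 11.1 says the form's data derive from the protocol.

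Stronger readings are tempting and are not supported. A reader might infer that the comparison of treatment-related toxicity between arms is invalid because the SBRT arm can have no related events. No such comparison is planned in section 8, and an all-cause comparison remains available; in an open-label trial (9.3) it is also less exposed to judgment. A reader might infer that worsening of existing disease after SBRT alone escapes the adverse event definition. The general definition in 7.2 already includes conditions associated with a procedure specified by the protocol, which can reasonably include SBRT.

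**Conclusion.** The point holds in a limited form. Table 10 is the only causality instrument in the plan. It cannot record SBRT, EBUS or surgery as a cause in any of the 20 planned patients, and it cannot record a joint cause in the 10 who receive the combination. Its yes criterion is stricter than its label, and its no criterion permits pneumonitis in irradiated lung to be coded as unrelated to pembrolizumab. The effect falls on attribution, on the provisions that depend on it, and on the record of action taken.

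The size cannot be put as a number: the documents do not say how often raters would choose no when two causes are plausible.

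A reader might infer that the safety conclusion in 8.1 is biased towards safe because pneumonitis could be coded away from the drug. The documents do not support that. Section 8.1 states no attribution filter, and under the literal reading its result does not depend on the coding. Its second sentence speaks of what the combined treatment results in, which is loose enough to merit one clarifying line, but it is not evidence of a filter.

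The conclusion assumes that the case report form will follow Table 10 and that no other causality scale exists outside the documents.

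**What to change.** 1. In Table 10 and on the adverse event form, record attribution separately for pembrolizumab, tracer, SBRT, EBUS and surgery, and allow more than one yes.
2. Align the yes and no criteria with the reasonable-possibility label, so that a plausible competing cause does not by itself give no.
3. Record action taken for SBRT and surgery as well as for the drug (for example interrupted, delayed or cancelled), in line with 7.1.2.1.
4. State in 8.1 that grade 3 or higher pneumonitis counts regardless of attribution.
5. Ask the investigators to reconcile 5.6.2.1 and 5.8.1 with multi-cause coding, because both now refer to drug-relatedness alone. How those sections should apply when SBRT is also suspected is a clinical decision for them.

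The cost is protocol wording and form fields, slightly more investigator work per event, and more events labelled as related. The last affects which events count as drug-related in Table 3 and 5.8.1, which is why item 5 belongs with the change.
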